9.2 Part 1, Arm B: EDT (letrozole and leuprolide)

MEMORIAL SLOAN-KETTERING CANCER CENTER IRB PROTOCOL

IRB#: 11-211 A(6)

Day 1 of Cycle 1: Baseline serum estrone, estradiol, testosterone and follicle-stimulating hormone (FSH) level in all patients (if not already done). If estradiol is within postmenopausal range for women (≤ 30 pg/mL) and testosterone is within the castration range for men (≤ 50 ng/dL), patient does not have to have hormones retested at week 2 and may begin letrozole 2.5 mg po QD Week 2 of Cycle 1.

- Day 1 of Cycle 1: Leuprolide 7.5 mg IM will be administered by a nurse in clinic.
- Week 2 of Cycle 1 (+/- 7 days): Women with estradiol not within postmenopausal range (≤ 30 pg/mL) or men with testosterone not within the castration range (≤ 50 ng/dL), measure serum estradiol and testosterone; if estradiol is within postmenopausal range (≤ 30 pg/mL) and testosterone is within the castration range (≤ 50 ng/dL), begin letrozole 2.5 mg po QD. Otherwise, retest hormones on C2W1. Consult MSKCC PI if hormones are still not within range. to further discuss the letrozole start date.
- Letrozole will be dispensed by the respective institutions' pharmacies and will be taken at home. Patients will be instructed to take letrozole at the same time each day, consistently with food or without food, and swallowed whole with a glass of water.
 - If a dose is missed, they will be instructed to take it as soon as they remember up until 12 hours past the schedule dose time. If it is almost time to take the next dose, they will be instructed to skip the missed dose and just take the scheduled dose. They will be instructed NOT to take 2 doses at the same time [137].
 - If vomiting occurs after taking letrozole, the subject should not take a replacement dose on that day. The subject should resume taking letrozole at the next scheduled dose on the following day. If vomiting persists, the subject should be instructed to notify the investigator. If a subject vomits what appears to be an intact tablet(s), the subject should not take a replacement dose on that day because it is not possible to determine how much drug has actually been absorbed.
 - Patients will be provided with a pill diary to record the date and time of day that letrozole was taken.
- Continue leuprolide 7.5 mg IM every 4 weeks (+/- 7 days).
- One cycle of EDT corresponds to 4 weeks of treatment.
- Letrozole and leuprolide should be administered concurrently at all times.

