^f In exceptional circumstances, which must be approved by the MSKCC principal investigator, week 3 visit can be schedule with a local oncologists along with the week 3 bloods

^g Includes Na, K, Cl, HCO₃, BUN, creatinine, glucose, AST, ALT, alkaline phosphatase.

^h Total and direct bilirubin, albumin. INR/PT/PTT is required at screening. For weeks 1 and 3 of each cycle, only PT/INR is required.

ⁱ To be repeated during weeks 1 and 3 of every cycle.

^j Only if Hepatitis B and/or C screening serologies are positive

^k Total cholesterol, triglycerides, LDL and HDL

^l To be repeated during week 1 of every cycle.

^m For patients on EDT, serum estradiol and testosterone only (FSH and estrone excluded). The post menopausal cutoff level for serum estradiol is $\leq 30 \text{ pg/mL}$. See sections 9.2, 9.3, or 9.4 for further clarification.

ⁿ For patients on EDT, the castration cutoff for testosterone is $< 50 \text{ ng/dL}$. See sections 9.2, 9.3, or 9.4 for further clarification.

^o For patients on EDT, may be performed at same time as other blood draws on C4W1, C7W1, C10W1, etc.

^p Includes specific gravity, color, turbidity, pH, albumin, glucose, ketones, bilirubin, blood, urobilinogen, leucocyte esterase, nitrite, and other findings

^q To be completed within 7 days of starting study therapy.

^r Or MRI abdomen/pelvis and non-contrast enhanced CT chest if patient allergic to CT contrast dye despite pre-medication, or other clinical contraindication.

^s Imaging studies performed at 6 months (+/- two weeks) will be used to determine the primary endpoint (PFS6)

MEMORIAL SLOAN-KETTERING CANCER CENTER
IRB PROTOCOL

IRB#: 11-211 A(6)

^tTumor aromatase and estrogen receptor expression, Ki67, and markers of mTOR activity (phospho-S6 kinase, phospho-Akt, cyclin D1) on biopsy specimens obtained before joining the study. For patients who undergo surgery on protocol therapy, tissue will be reexamined for same markers.

^u Left hand and wrist radiographs using the Greulich-Pyle Atlas.

^v If patient is randomized to Arm A, the Cycle 1 Week 2 visit can be scheduled with a local oncologist upon approval by the MSKCC principal investigator in exceptional circumstances.

^wAmmonia testing should be tested within 2 weeks before or on Cycle 1 Day 1 and at every visit when blood work is required.

Summary of evaluation plan during treatment

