Follow-up after study therapy

Patients who have discontinued the study will be asked to return four weeks later for an exit visit consisting of a medical history, vital signs, physical examination, toxicity check and blood tests including a complete blood count, Na, K, Cl, HCO₃, BUN, creatinine, glucose, AST, ALT, INR/PT/PTT, Ca, Mg, phosphorus, alkaline phosphatase, LDH, fasting blood glucose, fasting lipid panel, and ammonia. Patients who were on EDT will also be asked to provide blood to test serum estrogens, testosterone and FSH. After this exit visit, patients may be contacted every 3 months to monitor their survival. This information may also be checked through medical records or updated mortality lists of the institutions. Patients will also be encouraged to continue with periodic imaging after they have completed the study.

Correlative studies

Correlative studies are particularly important for rare diseases like FLL-HCC, and can be used to enhance the quantity and quality of information obtained from this study. Serum and tissue biomarker studies will be correlated with study outcomes to determine if they may have any predictive or prognostic value. Changes in biomarker expression in post-treatment specimens will also provide information about the precision of therapeutic targeting.

All specimens, including those procured at UCSF, JHU and DF/BWCC/MGHCC will be shipped to MSKCC or Labcorp and will be analyzed where the sample is sent.

- **Tissue biomarker analysis**

Tissue procurement and processing

- During screening, a block(s) of archived formalin-fixed paraffin-embedded FLL-HCC tumor tissue will be collected prior to the study and will be sent to the central laboratory facility at MSKCC along with the corresponding pathology report. Alternatively, approximately 20 unstained slides (if available) will be sent.
- Adequate samples should be sent to the pathology core lab facility at MSKCC, preferably within 4 weeks of beginning the study to permit adequate time to evaluate the samples and determine if additional samples are required.

MEMORIAL SLOAN-KETTERING CANCER CENTER IRB PROTOCOL

IRB#: 11-211 A(6)

- **For MSKCC patients:** samples are to be sent to the attention of [name], Department of Pathology, [name].
- **For participating sites:** samples are to be sent to the attention of Study 11-211, [name], [name].

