 - A 0.5 mL sample will be drawn into a red-top, gel-barrier, or EDTA tube provided by LabCorp. The serum should be separated and put into a plastic transfer tube and frozen immediately until it is ready to be shipped. All unsaturated vitamin B12 binding capacity samples will be processed at LabCorp [name]. Further details regarding sample preparation, packaging, and shipping are found in the study lab manual.
- **Serum des-γ-carboxyprothrombin (DCP)**
 - No special patient preparations are necessary.
 - A 2 mL sample will be drawn into a red-top or gel-barrier tube provided by LabCorp. The serum should be separated, put into a plastic transfer tube, and frozen immediately until it is ready to be shipped. All unsaturated serum DCP samples will be processed at LabCorp [name]. Further details regarding sample preparation, packaging, and shipping are found in the study lab manual.

Serum hormones

- All serum hormones will be processed and resulted at the respective site they were drawn at. Patients on the EDT-containing study arms (Arms B and C) will have blood drawn for the following serum hormones:
 - Serum estrone
 - Serum estradiol
 - Serum follicle stimulating hormone (FSH)
 - Serum testosterone
- Serum hormones will be measured within 2 weeks of initiating study therapy. Serum estradiol and testosterone will be measured again during Week 2 of therapy if required per protocol. All hormones (estrone, estradiol, FSH, testosterone) will be measured every 12 weeks thereafter.

• Sample storage and destruction

Blood and tumor samples collected for biomarker analysis and any other components from the cells may be stored for up to 20 years for future scientific investigations related to FLL-HCC. Study subjects maintain the right to have the sample material destroyed at any time by contacting the principal investigator. MSKCC will be the exclusive owner of any data, discoveries or derivative materials from the sample materials and is responsible for the destruction of the sample(s) at the request of the research subject through the principal investigator, at the end of the storage period, or as appropriate (e.g. the scientific rationale for experimentation with a certain sample type no longer

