- Following initiation of EDT, castration will be considered effective if serum estrogens are in the postmenopausal range, serum testosterone is in the castration range and FSH below the detection threshold as per the cutoffs established at the respective study site laboratories. The achievement of chemical castration will be correlated with PFS6.

- The maximum change in levels of tumor biomarkers from baseline will be correlated with PFS6.

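### Section 14 correlates achieved chemical castration with PFS6 without fixing which hormone draw counts, which opens the result to guarantee-time bias; a landmark at C4W1 closes it

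*Combined protocol and SAP*

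**What the plan says.** Section 14.0 (Biomarker analysis and data interpretation) treats castration as a composite, "effective if serum estrogens are in the postmenopausal range, serum testosterone is in the castration range and FSH below the detection threshold", and adds: "The achievement of chemical castration will be correlated with PFS6". It names no draw, time window or landmark, and no rule for a patient without a complete panel.

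The hormone schedule is spread over several places:

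- **Section 10.0, Serum hormones.** After the pretreatment draw, "Serum estradiol and testosterone will be measured again during Week 2 of therapy if required per protocol". Then: "All hormones (estrone, estradiol, FSH, testosterone) will be measured every 12 weeks thereafter".
- **Section 10.0, schedule footnotes.** Footnote m limits the early draw: "For patients on EDT, serum estradiol and testosterone only (FSH and estrone excluded". Footnote o says the 12-weekly draws "may be performed at same time as other blood draws on C4W1, C7W1, C10W1, etc".
- **Section 9.2.** If hormones are out of range at week 2: "Otherwise, retest hormones on C2W1".
- **Section 10.0, Follow-up after study therapy.** At the exit visit, four weeks after discontinuation: "Patients who were on EDT will also be asked to provide blood to test serum estrogens, testosterone and FSH".
- **Section 9.4.** Arm B patients who progress and enter Part 2 stay on EDT and keep the 12-weekly hormone schedule.

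Section 14.0 also counts anyone who comes off study before the 6-month scan as a PFS6 event.

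**The concern.** All components of the composite must be met, so it cannot be met on treatment before FSH and estrone are drawn. Estradiol and testosterone may be known at week 2 or C2W1; FSH and estrone are not. A patient who dies, progresses, withdraws or stops for toxicity before C4W1 has already failed on PFS6 and usually has no complete on-treatment panel. Every PFS6 success has stayed long enough to have one.

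Repeated draws tilt the comparison further. Both C4W1 and C7W1 fall before month 6, so a success has two chances to be recorded as castrated. A failure between those visits has one, and an earlier failure has none.

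If the classification rule lets this through, being recorded as castrated partly means having stayed on study for 12 weeks. Suppression of estrogen production is one of the two mechanisms in the trial's hypothesis, so a spurious association could be read as support for it.

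**Working it through.** **Plan's own figures.** The documents give no figure for this correlation. The PFS6 rates and sample sizes used here come from the Simon design in section 14.0 (stop at 6 or fewer of 16; promising at 15 or more of 28; 40% v 64%). Exact binomial calculation gives early termination P(X ≤ 6 | 16, 0.40) = 52.7% (stated 53%), type I error 9.9% and power 90.2% (both errors set at 10%). The design reproduces.

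**Timing.** Cycles last 4 weeks. C4W1 follows three cycles: 3 × 4 = 12 weeks. C7W1 follows six: 6 × 4 = 24 weeks, before the 6-month point at about 26 weeks.

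**Assumptions not in the documents.** Arms B and C are pooled (2 × 28 = 56 patients at most; 2 × 16 = 32 if both stop at stage 1). 80% are truly castrated, independently of outcome, so there is no true effect. The test is a two-sided Fisher's exact test at 0.05. Section 14.0 names that test for categorical baseline serum markers, not for castration.

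**Apparent effect.** Let S be PFS6, c the true castration rate and e the share failing before C4W1, all of them recorded as not castrated.

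- PFS6 in recorded castrated = S / (1 − e)
- PFS6 in recorded not castrated = S(1 − c) / [1 − c(1 − e)]

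Example with S = 0.40, c = 0.80, e = 0.10: 0.40/0.90 = 44.4% against 0.08/0.28 = 28.6%, with no true effect.

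If failure were exponential and observed continuously, e = 1 − 0.40^(12/26) = 34.5%.

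**False-positive rate by simulation, 56 patients, PFS6 40%, 80% castrated.** Ranges show the spread between repeated runs.

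| Early-failure share | PFS6, castrated v not (all misrecorded) | False positives, all misrecorded | False positives, half misrecorded |
|---|---|---|---|
| 5% | 42.1% v 33.3% | 5–6% | 3–4% |
| 10% | 44.4% v 28.6% | 13–14% | 5–6% |
| 15% | 47.1% v 25.0% | 28–29% | 9% |
| 34.5% | 61.1% v 16.8% | 91–92% | 36–38% |

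At PFS6 64%, with all misrecorded, the rates are about 12%, 37% and 67% at shares of 5%, 10% and 15%. With 32 patients at PFS6 40% they are about 3%, 8% and 15%, and about 66% at 34.5%.

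**With a C4W1 landmark.** Early failures leave both groups, so under no effect PFS6 is S/(1 − e) in each. The false-positive rate is about 3% in every 56-patient row above.

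**The case against.** The strongest reply is that the plan is silent rather than wrong. Nothing says that a missing panel means not castrated. Section 14.0 analyses changes in serum markers separately at each collection time. If castration were handled that way, a patient with no C4W1 sample would drop out, which is close to a landmark analysis. That is a fair reading, but castration has its own line, as a single achieved status with no time point, so the harmful readings remain open.

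Four stronger inferences are tempting, and the documents do not support them.

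- **That all the hormones wait until week 12.** Only FSH and estrone do.
- **That no early failure can be recorded as castrated on therapy.** Arm B progressors in Part 2 stay on EDT with 12-weekly panels. Arm C has no such route, nor do patients who die, withdraw or stop for toxicity. Whether a post-progression panel counts is not stated.
- **That the exit panel will read as not castrated.** Section 5.3 gives letrozole a half-life of 2–4 days, but no passage gives hormone recovery four weeks after leuprolide. The one recovery time given, in section 3.5.6, is menses returning after a mean of 16 months in girls treated with a GnRH agonist. The exit panel is off therapy and may mislead; how often is unknown.
- **That about a third of patients fail before the panel.** In section 16.1.1.4 the RECIST form first appears at Cycle 4+. In the section 10.0 table the on-treatment CT mark sits in the same position as the 12-weekly tumor-marker mark, although the columns look shifted. Both suggest first scheduled imaging near week 12. Early failures would then be mainly deaths, clinical progression, withdrawals and unscheduled scans, for which no rate is given.

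The analysis is also one correlative among several, and no stopping or selection rule uses it. That limits its weight but does not remove the gap.

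**Conclusion.** The concern holds in conditional form. As written, the analysis is open to guarantee-time bias toward a benefit of castration. The bias arises if missing panels count as not castrated, if misleading exit draws are used, or if status means ever achieved; the third route was not simulated, and only its direction is claimed.

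The size turns on the early-failure share. At 5% the false-positive rate is close to nominal; at 10–15% it is roughly 14–29% under full misrecording. A reader might take the figure above 90% as the expected size, but it needs continuous exponential failure and every early failure misrecorded, and the schedule points away from the first of these. All figures also rest on 80% true castration, pooled arms and Fisher's test. The direction does not depend on the choice of test. The primary PFS6 decision is untouched.

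**What to change.** In section 14.0, define castration status by the single C4W1 on-treatment panel of estrone, estradiol, testosterone and FSH. Relate it to PFS6 only among Arm B and C patients who are on study and progression-free at that landmark. State that exit-visit draws, post-progression Part 2 draws and later panels are not used to classify status. Report how many patients were excluded for early failure and how many lacked a C4W1 panel.

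The cost is a few sentences of analysis text and no new blood tests. The downside is that patients who fail before week 12 leave this one correlative analysis, so it says nothing about castration and very early failure.

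An earlier landmark at C2W1 is not preferable. It would need FSH and estrone added to that draw. Under section 4.3 and footnote e of the section 10.0 schedule, some patients may start letrozole only around that visit, so their status would be fixed before the full regimen had acted.

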- If everolimus or both EDT drugs must be completely discontinued, patient will be declared off trial. However, if a patient is able to tolerate either component of combined therapy (ie. Everolimus or EDT) but not both, and is experiencing clinical benefit, the study chair may allow continuation of everolimus or EDT pending the approval of the local IRB.
- Treatment will continue until disease progression, global clinical deterioration, unacceptable toxicity and/or consent withdrawal.
- Therapy may be held for a maximum of 4 weeks to recover from toxicity (see Sections 9.5 through 9.8)

9.4 Part 2: Combined therapy with everolimus and EDT after progression on either everolimus or EDT alone

- Patients who develop disease progression on either Arm A or B during Part 1 of the study will proceed to combined therapy.
 - At the start of Part 2 the last CT scan on Part I will be used as the baseline scan for RECIST 1.1 criteria.

Patients who were on everolimus (Arm A) during Part 1 will begin EDT with leuprolide 7.5 mg IM .

- Patients who required a dose reduction on Arm A during Part 1 will continue at the reduced dose level for Part 2.
- Day 1 of Cycle 1: Baseline serum estrone, estradiol, testosterone and follicle-stimulating hormone (FSH) level in all patients. If estradiol is within postmenopausal range for women (≤ 30 pg/mL) and testosterone is within the castration range for men (≤ 50 ng/dL), the patient does not have to have hormones retested at week 2 and maybe begin letrozole 2.5 mg po QD Week 2 of Cycle 1.
 - Week 2 of Cycle 1 (+/- 7 days): Women with estradiol not within postmenopausal range (≤ 30 pg/mL) or men with testosterone not within the castration range measure serum estradiol and testosterone; if estradiol is within postmenopausal range (women) or testosterone is within the castration range (men), begin letrozole 2.5 mg po QD. Otherwise, retest hormones on C2W1. Consult MSKCC PI if hormones are still not within range. to further discuss the letrozole start date.
 - Leuprolide 7.5 mg IM will be administered every 4 weeks (+/- 7 days).

Patients who were on EDT (Arm B) during Part 1 will begin everolimus on Day 1 of Part 2 of the study at the following doses:

- Patients with a BSA $\leq 1.5 \text{ m}^2$ will receive everolimus 5 mg PO QD.
- Patients with a BSA $> 1.5 \text{ m}^2$ will receive everolimus 7.5 mg PO QD.
- Patients should continue with their every 12 weeks hormone testing schedule from Arm B.

All Patients on Part II

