 - Phospho-S6 (phosphorylated ribosomal protein S6)
 - Phospho-Akt
 - Cyclin D1
- Evaluation of the tumor specimens and description of staining intensity will be performed by [name].
- The baseline staining pattern for the various markers will be correlated with progression-free survival at 6 months (PFS6).
- Immunostains will be repeated on tumor specimens obtained from patients who undergo surgery on protocol therapy. Changes in tissue biomarkers from baseline to surgery will be summarized descriptively.

Blood biomarkers

Blood samples for future research

- Two tubes of blood for plasma and serum to be used in future research studies at MSKCC will be collected from all patients
 - Kits for these samples will be provided to each participating site by MSKCC and collected plasma and serum samples will be bulk shipped to MSKCC every six months.
 - Instructions for processing these samples, as well as shipment information, are in the Lab Manual.

Putative FLL-HCC tumor biomarkers to be measured within 2 weeks of initiating study therapy and every 12 weeks during the protocol in all patients.

- **AFP**
 - AFP will be collected and resulted at respective site's laboratory.
- **Plasma neurotensin**
 - **Patients should be fasting 10 - 12 hours prior to collection of specimen. Patients should not be on any antacid medication or medications that affect gastroentero-intestinal function, if possible, for at least 48 hours prior to collection.**
 - A 10mL sample will be drawn into an EDTA z top tube provided by the Interscience Institute through LabCorp. The serum should be separated from the whole blood as soon as possible to maintain the integrity of the sample. Once the serum has been

MEMORIAL SLOAN-KETTERING CANCER CENTER IRB PROTOCOL

IRB#: 11-211 A(6)

separated it should be frozen immediately until the sample is ready to be shipped. All neurotensin samples will be processed at Inter Science Institute [name]. Further details regarding sample preparation, packaging, and shipping are found in the study lab manual.

- **Serum unsaturated vitamin B12 binding capacity (transcobalamin)**
 - **Must draw before Schilling test, transfusions, or B₁₂ therapy is started.**

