14.0 BIOSTATISTICS

Primary efficacy endpoints for Part 1 of protocol

- The primary efficacy endpoints for Part 1 of the study is progression-free survival at 6 months (PFS6).
- A progression event refers to the first evidence of radiographic disease progression, clinical progression as determined by study investigators, or death.
- Imaging performed in 6 months will be used to determine PFS6.
- PFS6 will be defined as the percentage of patients who are alive and have not experienced a progression event as defined above at 6 months from the date that study therapy was initiated. Patients that come off study before the 6 months scan will be considered events for the primary endpoint analysis.
- PFS6 will be assessed using a Simon's minimax two stage design, hypothesizing an improvement in PFS6 from 40% to 64% with the study regimen. Sixteen patients will be enrolled onto each of Arms A, B and C for a total of 48 patients in the first stage. Accrual will stop till the progression status at 6 months is obtained on all 16 patients in each arm. If 6 or less patients in one arm are progression free at 6 months the regimen in that arm will be terminated; otherwise, if 7 or more patients are alive and progression free at 6 months, enrollment will be extended in that arm to 28 patients (maximum total of 84 patients). At the end of stage 2, the respective regimens will be declared promising if 15 or more of the 28 patients in each arm are alive and progression free at 6 months. The design assumes a type I error (falsely accepting a non-promising therapy) and type II error (falsely rejecting a promising therapy) both set to 10%.

Figure 4: Simon's minimax 2 stage design (schematic applicable for each study arm)

- The probability of early termination due to drug inefficacy is 53%. In the event that 2 or more arms show promising activity, we will use the “pick the winner” format based on the randomized phase II clinical trials approach proposed by Simon et al. In this case, the regimen that has at least 15 patients progression free at 6 months and exceeds by at least 2 patients the number of progression free patients in the second best arm would be declared the winner. The probability of selecting the better regimen is 85%; the probability that no regimen is selected is 7%, while the probability of a tie is approximately 6% [149].

Secondary endpoints

- Secondary endpoints are:
 - Median PFS
 - Median overall survival (OS)

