 - Objective response rate by RECIST 1.1 guidelines
 - Rate of conversion to resectable status
 - Safety and toxicity
 - Correlative serum and tissue biomarker studies.
- Kaplan-Meier PFS will be measured from the date that study therapy is initiated until the date of

first evidence of radiographic disease progression, global clinical deterioration as determined by study investigators, or death.

- Kaplan-Meier OS will be measured from the date that study therapy was commenced until the date of death.
- Objective responses will be reported using RECIST guidelines (version 1.1). Objective response will be estimated using binomial proportions and exact 95% CIs will be provided.
- Conversion to resectable status to be determined by hepatobiliary surgeons in conjunction with radiological assessment of response to therapy.
- Adverse events/toxicity will be monitored and recorded using the CTCAE version 4.0 and summarized descriptively.
- Baseline serum measurements will be correlated with PFS6 (binary endpoint) using Fisher's exact test for categorical serum measurements and using Wilcoxon rank sum test for continuous measurements. For each time point at which serum measurements are collected, changes in the different binary serum markers from baseline will be correlated with PFS6 using conditional logistic regression to account for the paired nature of the data while Wilcoxon signed-rank test will be used for continuous measurements.
- Associations between baseline tissue biomarkers and PFS6 will be assessed using Fisher's exact test for categorical biomarkers, trend tests for ordinal biomarkers and Wilcoxon rank-sum test for continuous biomarkers. For patients undergoing surgery, changes in tissue biomarkers from baseline to surgery will be summarized descriptively in an exploratory fashion.

Exploratory analysis for Part 2 of protocol (combination therapy).

- PFS will be evaluated for patients who were on Arm A (everolimus) or Arm B (EDT) during Part 1 of the study who subsequently received combined everolimus + EDT during Part 2.
- PFS will be measured as the time from the start of the combination therapy till progression or death whichever comes first.

Biomarker analysis and data interpretation

- Baseline tissue biomarkers will be correlated with PFS6.
- Baseline levels of hormones will be correlated with PFS6.
- Baseline levels of tumor markers will be correlated with PFS6.

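### Correlating the maximum tumor-marker change with PFS6 lets the outcome set how many draws enter the maximum, so on Part 1 draws an uninformative marker can look associated

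*Combined protocol and SAP*

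**What the plan says.** The last item under the biomarker heading of section 14.0 reads "The maximum change in levels of tumor biomarkers from baseline will be correlated with PFS6". It gives no time window, no sign for the change, no test, no rule for a patient without a post-baseline draw, and no statement on whether Part 2 draws count.

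The schedule is in section 10.0. Under Blood biomarkers, the tumor markers are measured within 2 weeks of starting therapy and "every 12 weeks during the protocol in all patients". Footnote o of the table, which is worded for patients on EDT, says the draws "may be performed at same time as other blood draws on C4W1, C7W1, C10W1, etc". With 4-week cycles these visits fall at about weeks 12, 24 and 36. Sections 9.1 to 9.3 continue Part 1 treatment until progression, clinical deterioration, unacceptable toxicity or withdrawal.

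For the primary endpoint, section 14.0 adds: "Patients that come off study before the 6 months scan will be considered events for the primary endpoint analysis".

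A separate item under the secondary endpoints plans analyses by visit: "For each time point at which serum measurements are collected, changes in the different binary serum markers from baseline will be correlated with PFS6", by conditional logistic regression. For continuous markers, "Wilcoxon signed-rank test will be used for continuous measurements".

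On Part 2, section 9.4 says "Patients who develop disease progression on either Arm A or B during Part 1 of the study will proceed to combined therapy", whereas section 4.2 says only that they may. Arm C has no Part 2.

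**The concern.** PFS6 status partly determines how many values enter the maximum. On Part 1 draws, a success has two by week 24 and goes on adding more. A failure stops being drawn at or before progression. The maximum of several noisy values tends to exceed the maximum of fewer, so successes will tend to show the larger maximum change even if the marker carries no information.

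Biomarkers are a listed secondary objective (section 2.3), and section 10.0 says the correlations will be used to judge predictive or prognostic value. In a disease this rare, a spurious marker would be hard to refute with later data.

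**Working it through.** **Inputs from the documents.** PFS6 40% (null) and 64% (target); 16 patients per arm, extended to 28 if 7 or more are progression-free; 15 or more of 28 is promising; maximum 84 (section 14.0). Draws every 12 weeks (section 10.0).

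**Assumed, not in the documents.** Two-sided 5% level; Wilcoxon rank-sum test (section 14.0 names it for continuous baseline serum measurements, not for this item); exponential PFS; normal changes from baseline with a common between-draw correlation r; pooling of arms where N exceeds 28. The imaging interval cannot be read reliably from the schedule table, so two timings were used: progression found at 12-weekly scans with a draw at that visit, and progression between scans with draws only beforehand.

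**Step 1: the plan's own figures.** P(6 or fewer of 16 at 40%) = 0.527, matching the stated 53%. The design has type I error 9.9% and power 90.2%, matching 10% and 10%. The plan gives no figure for the biomarker analysis.

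**Step 2: draws among failures, Part 1 only, to week 24.**
- Scan-timed, with PFS6 = p set at week 24: the share with one draw is (1 − √p)/(1 − p), which is 0.368/0.60 = 61% at p = 0.40 and 0.20/0.36 = 56% at p = 0.64. The other 39-45% have two.
- Between scans, with failure by week 26: the share with no draw is (1 − p^(12/26))/(1 − p), which is 0.345/0.60 = 58% and 0.186/0.36 = 52%. A further 38-42% have one and 5-6% have two.

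Every success has two.

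**Step 3: size of the artefact by hand (scan-timed, signed maximum, week-24 cut).** For two standardised changes with correlation r, the expected maximum is √((1 − r)/π) SD; for one draw it is 0. The mean gap between PFS6 groups is that value times the share of failures with one draw. At p = 0.40 and N = 84 there are 33.6 successes and 50.4 failures, so SE = √(1/33.6 + 1/50.4) = 0.223. The normal approximation to the rejection rate is P(|Z + gap/SE| > 1.96).

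| r | expected maximum | gap (×0.613) | gap/SE | by hand | simulated |
|---|---|---|---|---|---|
| 0.5 | 0.399 | 0.244 | 1.10 | 19.5% | 18.5% |
| 0.8 | 0.252 | 0.155 | 0.69 | 10.7% | 10.0% |
| 0.95 | 0.126 | 0.077 | 0.35 | 6.4% | 5.8% |

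At N = 28 the SE is 0.386 and the same formula gives 9.7%, 6.9% and 5.5%.

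**Step 4: null simulation over both timings and both PFS6 rates.**

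| Reading of the rule | N = 84 | N = 28 |
|---|---|---|
| Signed, Part 1 to week 24, r 0.5-0.8 | about 8-23% | 6-10% |
| Same, r 0.95 | about 5-7% | near 5% |
| Absolute, Part 1 to week 24, r 0.5-0.8 | about 13-38% | 7-16% |
| Signed, Part 1 to about one year, r 0.5-0.8 | about 22-68% | 9-26% |
| Same, r 0.95 | about 8-12% | not tabulated |
| Signed, to week 24, all Arm A/B failures add Part 2 draws | 5-7% | 4-6% |
| Week-12 landmark | about 3-6% | about 3-6% |

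If only 60% of Arm A and B failures cross over, the week-24 figure at N = 84 is 6-10%. If Part 2 draws count with no window, it is 16-36% (N = 84, PFS6 40%, r 0.5-0.8, assumed median 24 weeks in Part 2).

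**Step 5: the realistic N.** P(an arm continues) is 0.473 at 40% and 0.972 at 64%. All three arms reach 28 with probability 0.473³ = 0.106 or 0.972³ = 0.918. Mean N = 48 + 36 × 0.473 = 65 or 48 + 36 × 0.972 = 83. At the N the two-stage rule produces, the week-24 signed rate is 9-20% for r 0.5-0.8.

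**The case against.** **The size is not the plan's.** The item says only that the two will be correlated. The test, the 5% level, pooling and r are all assumed. With very stable markers (r 0.95) and a week-24 cut the effect nearly vanishes, and in one arm it is modest. This stands as to size. The direction does not depend on these choices.

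**Part 2 draws may count.** Section 10.0 speaks of draws during the protocol, and section 9.4 sends Arm A and B progressors on to combined therapy. With a week-24 cut and near-complete crossover the problem largely goes. But the plan states no cut, section 4.2 makes Part 2 optional (the two sections need reconciling), Arm C has none, and Part 2 values reflect a different regimen.

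**The by-visit analysis already covers it.** It gives a fixed-time analysis for binary markers. For continuous markers, the signed-rank test compares change with zero and does not compare PFS6 groups. It stands beside the maximum-change item and does not replace it.

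**Off-study coding applies to the primary analysis only.** Carrying it to the biomarkers is an inference. The mechanism does not need it, because progressors have fewer Part 1 draws in any case.

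**A stronger reading.** A reader might infer that the PFS6 result or the choice of arm is compromised, or that a false association is near certain. The documents do not support either. No stopping, treatment or selection rule uses this correlation, and the highest rates need an open-ended window, pooling and only moderate correlation between draws.

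**Conclusion.** The concern holds in a bounded form. Followed as written and applied to Part 1 draws, the maximum-change rule builds in a tendency for PFS6 successes to show larger changes, whatever the marker. The inflation above 5% ranges from negligible (week-24 cut with r 0.95, or nearly complete Part 2 draws) to severe (open-ended maximum in the pooled sample). Fixing only the sign and a week-24 window would not be enough for a pooled analysis with r 0.5-0.8, since the 8-23% already assumes both.

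The consequence is confined to a correlative secondary analysis. It merits correction because the remedy is cheap and the result is meant to inform predictive or prognostic claims.

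**What to change.** In section 14.0, replace the maximum change with the signed change from baseline at the week-12 (C4W1) draw, in Part 1 patients alive and progression-free at week 12. Relate it to their later PFS6 status or to PFS measured from week 12. Name the test. Use later values only as time-dependent covariates, exclude Part 2 draws, report how many patients have no draw, and label the analysis exploratory.

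**Cost.** No new samples. The rule sits in the protocol, so the change is a wording amendment needing approval by the coordinating IRB and, unless expedited, the site IRBs (section 16.3.1).

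**Downside.** Patients failing before week 12 leave this analysis, and the question becomes one about those still progression-free then. The share remaining is p^(12/26) = 0.655 at 40% and 0.814 at 64%. Of 84 that is about 55 or 68, with about 84 × (0.655 − 0.40) = 21 or 84 × (0.814 − 0.64) = 15 later failures. In one arm it is about 18 or 23 of 28, with about 7 or 5 later failures.

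Power for a 0.8 SD difference is about 74-80% at N = 84. At PFS6 40% it is about 67% at N = 65 and 51-53% at N = 48. In a single arm it is about 30%.
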